5.1.2 Regimen Description and Guidelines for Drug Administration

Treatment will be administered on an outpatient basis. All patients will take the oral ACY-1215 160mg for 28 consecutive days on a 28-day treatment cycle. Frequency in phase II will be determined based on Phase Ib results. ACY-1215 will be supplied as a liquid for oral administration (PO). Each dose will be administered at least 1 hour after ingestion of food and followed by at least 4 ounces of water. Patients will be instructed not to ingest food or other oral medication for at least 2 hours after each ACY-1215 dose. Reported adverse events and potential risks for oral ACY-1215 are described in Section 7. Appropriate dose modifications are described in Section 6. No investigational or commercial agents or therapies other than those described may be administered with the intent to treat the patient's malignancy.

5.1.2.1 Rationale for the Dose Selected

In this study, ACY-1215 will be examined as a single agent administered by the oral route 28 consecutive days of a 28 day cycle in patients with relapsed and/or relapsed-refractory lymphoma to assess clinical response, safety, tolerability, PK and PD of ACY-1215.

The rationale of the dosing schedule of ACY 1215 is based on results from a Phase I monotherapy trial in which no maximally tolerated dose (MTD) was established when ACY-1215 was dosed once daily on days 1-5 and days 8-13 of a 21 day cycle up to a dose of 360 mg. Pharmacokinetics were similar at doses of 160 mg (C_{max} 626 +/- 150 ng/mL and $AUC_{0-\infty}$ 1300 +/- 533 ng*h/mL) to higher doses. The half-life of elimination ranged from 3-4 hours and no

accumulation of drug was observed. Dosing at 160 mg and above demonstrated acetylation of tubulin, the pharmacodynamic marker of HDAC6 inhibition, in peripheral mononuclear cells for all patients in these cohorts. Doses above 160 mg lead to off target effects demonstrated by acetylation of histone 3 and increased toxicities. Given the relatively short half-life (~3 h) and safety profile of ACY-1215, twice daily dosing will also be explored to maximize the dose intensity while limiting the toxicity. Twice daily administration of ACY-1215 at 160 mg is expected to approximately double the daily exposure (AUC) to ~4000 ng·h/mL with a minimal impact on maximal plasma levels and no anticipated accumulation, since >95% of the administered dose will have been cleared before the next dose administration. 28-day repeat dose GLP toxicology studies in dogs showed that exposure levels of 15,000-26,800 ng·h/mL were attained with minimal to mild changes in blood cell parameters and minimal changes in body weight that were partially to fully recoverable. Twice daily dosing is therefore not anticipated to change the safety profile of ACY-1215. Accordingly, once daily and BID dosing at 160 mg will be explored in the Phase 1b section of the trial.

5.1.2.2 Rationale and Justification of the Study Design

The trial design is based on existing data recently obtained from a Phase 1-2 study of ACY1215 in patients with multiple myeloma. In nonclinical studies, ACY-1215 has been shown to induce cellular cytotoxicity in MM and lymphoma cells as a single agent. Thus, the anti-tumor activity of ACY-1215 will be studied in patients with lymphoma.

Given that the experience of ACY-1215 monotherapy is limited and restricted to multiple myeloma patients only, a Phase Ib study will be performed. In prior Phase I study, dose limiting toxicities were never reached, although pharmacodynamics endpoints were met and pharmacokinetic profile plateaued at 160 mg daily dosing. This current study is designed to evaluate two dosing schedules of the recommended dose (160 mg see above Section 2.2.14) for safety and tolerability while maximizing intensity of exposure to the study drug. It will inform the final dosing schedule to be used in the Phase II. The total possible number of patients to be accrued to the Phase Ib is 20 if each cohort is expanded to 10 patients.

The Phase II study will be designed to determine the efficacy of ACY-1215 in lymphoid malignancies and incorporated an expansion cohort of patients with mantle cell lymphoma. The minimum number of patients to be treated in stage 1 of the Phase II part is consistent with this standard minimax Simon-2stage design. In order to ensure the safety of patients, the Sponsor personnel, the Study Chair, and Investigators will review all safety data from the first stage before enrollment of additional patients into stage 2 and the expansion cohort. The expansion cohort of patients with mantle cell lymphoma was chosen to obtain early activity and response data in this specific subtype. This subtype was chosen given its sensitivity to bortezomib, a drug which inhibits catabolism of unfolded proteins and which has single agent activity in mantle cell lymphoma.

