4.4 Registration Process

To register a patient, the following documents should be completed by a member of the research staff and sent to the study coordinator at CUMC:

- Eligibility Screening Worksheet
- Copy of required laboratory and imaging tests

The Study Coordinator will verify eligibility. To complete the registration process, the Coordinator will:

- Assign a patient study number
- Register the patient on the study
- Confirm registration with the Principal Investigator

No patient may be enrolled or begin treatment prior to registration and assignment of a patient number. Patients who are registered but not treated will be replaced. Investigators will be notified by CUMC when enrollment in the initial part of the study(stage 1) is closed and enrollment into the next parts of the study (stage 2 and expansion cohort) can begin. Investigators will be notified by CUMC or the Sponsor if the study is placed on administrative hold, when it is completed, or is closed to further patient enrollment.

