11.2 Data Safety Monitoring Board

The Herbert Irving Comprehensive Cancer Center at Columbia University Medical Center's Data Safety Monitoring Board (DSMB) will oversee conduct of the study, patient safety and all interim analyses as specified in the data analysis plan. Detailed guidelines regarding the structure, function and decision-making mechanisms for the Data Safety Monitoring Board are provided in the DSMB charter.

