12.1 Statistical Methods

12.1.1 Phase Ib:

The study will follow the similar principles of a standard 3+3 dose escalation study in which less than one third of patients enrolled to a particular Arm must not have a dose limiting toxicity to allow for expansion. Three patients will be sequentially enrolled in one of two cohorts: Arm A and then after a safety assessment has occurred, Arm B for a total of six patients (3 in each arm). If $\leq 33\%$ of patients ($N \leq 1$) experiences a dose limiting toxicity (DLT) in a cohort, the cohort will be expanded to 6 patients. If there are $\leq 33\%$ ($N \leq 2$ DLTs), the cohort will be further expanded to a total of 10 patients (3+3+4). The total number of patients for both Arms A and B with full expansions will total of 20. If more than 1/3 or 2/6 patients experience a DLT, there will be no expansion. Safety data obtained from this Phase Ib will be analyzed by the sponsor and collaborating investigators to recommend a Phase II dose.

12.1.2 Phase II:

The study will employ the minimax Simon 2-stage design. In Stage 1, 22 patients will be enrolled. If < 2 patients experience an objective tumor response (defined as CR, or PR, as outlined by the 2007 International Harmonization Project criteria), the study will be discontinued. If 2 or more of the first 22 patients experiences CR, or PR, additional 18 patients will be enrolled in Stage 2. Enrollment into Stage 2 will begin only after least 2 objective response have been observed in Stage 1. (Enrollment into Stage 2 need not be delayed until the response status of all 22 Stage 1 patients is known.) The design parameters are as follows:

- 0.15: unacceptable response rate.

- 0.25: target response rate.
- $\alpha = 0.05$: the probability of declaring the drug effective when the true response probability is less or equal to 0.15.
- $\beta = 0.20$: the probability of declaring the drug as not effective when its true response probability is as large or larger than the target response rate 0.30.

Once enrollment begins for stage 2 of the study, an additional 20 patients will be enrolled per lymphoma subtype, specifically Mantle Cell Lymphoma. Therefore the total number of patients estimated to be enrolled is 60.

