12.9 Analysis Schedule

12.9.1 Interim Analysis

12.9.1.1 Phase Ib

Upon enrollment of three patients into Arm A and then after a safety assessment has occurred,

Arm B, no additional patients will be accrued until completion of cycle one to adequately evaluate for dose limiting toxicities. Following determination of <1/3 of patients experiencing a DLT 3 additional patients will be enrolled for a total of 6 patients per Arm. If < 1/3 or < 2/6 patients experience a DLT, planned accrual will expand to a maximum of 10 patients in each arm. The Phase II study will not begin until all 10 patients have completed one full cycle of therapy.

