12.9.1.2 Phase II

Interim analysis will be performed following accrual of the first 22 patients to ensure a response rate of at least 10% to proceed to stage 2 of accrual. An early stopping rule will be in effect if <10% of patients achieve a response. If >10% achieve a response, Stage 2 will proceed.

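### The Stage 1 safety review promised in Section 5.1.2.2 is missing from the Section 12 rules that open Stage 2 and the mantle cell cohort, and it has no data cut

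*Combined protocol and SAP*

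**What the plan says.** Section 5.1.2.2 sets a safety condition on going further: sponsor personnel, the Study Chair and the investigators "will review all safety data from the first stage before enrollment of additional patients into stage 2 and the expansion cohort". It gives no data cut, minimum follow-up or decision criterion.

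Section 12.1.2 gives the working rule. If at least 2 of the first 22 patients respond, 18 more are enrolled. It adds "Enrollment into Stage 2 will begin only after least 2 objective response have been observed in Stage 1", and then "Enrollment into Stage 2 need not be delayed until the response status of all 22 Stage 1 patients is known". The MCL cohort follows from the same event: "Once enrollment begins for stage 2 of the study, an additional 20 patients will be enrolled per lymphoma subtype, specifically Mantle Cell Lymphoma".

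Section 12.9.1.2 places the check at accrual: "Interim analysis will be performed following accrual of the first 22 patients to ensure a response rate of at least 10" per cent. It then says that Stage 2 goes ahead if more than 10% respond. Neither part of Section 12 mentions the safety review.

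Three other places bear on the point:
- Section 4.4 gives the coordinating center control of opening: "Investigators will be notified by CUMC when enrollment in the initial part of the study(stage 1) is closed" and the next parts can begin.
- Section 11.2 says that the DSMB "will oversee conduct of the study, patient safety and all interim analyses as specified in the data analysis plan".
- Section 12.9.1.1 shows how the protocol writes a safety hold when it means one. In Phase Ib, "no additional patients will be accrued until completion of cycle one to adequately evaluate for dose limiting toxicities".

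**The concern.** The safety condition stands in one sentence of a rationale section. The rules that a coordinator or statistician would apply stand in Section 12 and depend only on response. Someone following Section 12 as written would open Stage 2 and the MCL cohort without meeting the safety review, or would hold it while the most recent Stage 1 patients were still in their first cycle.

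Opening Stage 2 allows up to 18 + 20 = 38 further patients. Phase Ib contributes at most 10 patients on whichever schedule is chosen, so the 22 Stage 1 patients are the larger body of safety evidence on that schedule. The review is worth most if it covers all of them for a defined period.

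**Working it through.** The documents give no figure for the completeness of the safety data at this step, so there is none to reproduce.

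**Inputs**
- Stage 1, Stage 2 and MCL sizes of 22, 18 and 20 (Section 5.1.2, Phase II).
- Average accrual of 6 per month, with accrual to be completed in 12 to 18 months (Section 13).
- 28-day cycles (Table 1); first scan within 7 days before cycle 3 (Section 10.1), taken here as day 56.
- Response rates of 0.15, 0.25 and 0.30 (all three appear in Section 12.1.2).
- Assumed: evenly spaced accrual, a 30.44-day month, every response seen at the first scan, and a cycle-1 toxicity rate of 10% (range 5% to 20%).

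**1. Patients still in cycle 1 when the 22nd enters**

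Patients in cycle 1 = accrual per day × 28.
- At 6 per month: 6/30.44 = 0.197 per day; 0.197 × 28 = 5.5. Over two cycles, 0.197 × 56 = 11.0 have not finished cycle 2.
- At 60 patients in 18 months: 60/18 = 3.33 per month; 3.33/30.44 × 28 = 3.1.

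At 6 per month, patients enter every 5.07 days and the 22nd enters on day 21 × 5.07 = 106.5. Sixteen patients have completed 28 days by then.

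**2. Would the response rule itself impose a wait?**

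Only patients entered at least 56 days earlier have been scanned. By day 106.5 that is the first 10 patients. By day 134.5, when the 22nd completes cycle 1, it is the first 16. The chance that the second response has been seen by then, given that the two-response rule is eventually met, is P(at least 2 of k) / P(at least 2 of 22).

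| True response rate | By entry of the 22nd (k = 10) | By the 22nd's end of cycle 1 (k = 16) |
|---|---|---|
| 0.15 | 0.456/0.863 = 53% | 0.716/0.863 = 83% |
| 0.25 | 0.756/0.985 = 77% | 0.937/0.985 = 95% |
| 0.30 | 0.851/0.996 = 85% | 0.974/0.996 = 98% |

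So the response rule will usually not hold Stage 2 back until Stage 1 has completed cycle 1.

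**3. What the missing follow-up costs**

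P(at least 2 cases in n) = 1 − (1 − p)^n − n·p·(1 − p)^(n−1).

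With p = 0.10 and n = 22: 1 − 0.0985 − 0.2407 = 0.66. With n = 16: 1 − 0.1853 − 0.3294 = 0.49.

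The n = 16 figure gives no credit to the 6 patients still in cycle 1. At half credit each, n = 16 + 3 = 19: 1 − 0.1351 − 0.2852 = 0.58.

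| Assumed toxicity rate | All 22 through cycle 1 | Half credit (n = 19) | No credit (n = 16) |
|---|---|---|---|
| 5% | 30% | 25% | 19% |
| 10% | 66% | 58% | 49% |
| 20% | 95% | 92% | 86% |

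At 3.33 per month about 19 of the 22 are fully followed. Even with no credit for the other 3, the 10% row then gives 58%.

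**The case against.** The strongest reply is that nothing conflicts. Section 12.1.2 makes two responses a necessary condition, and its waiver covers response status only. Section 5.1.2.2 adds a second condition, and a site can obey both. Most of this stands. A reader might infer that Section 12 overrides the safety review, or that Stage 2 opens without waiting for Stage 1 patients at all. The text supports neither: the waiver does not mention safety data, it dispenses only with knowing the response of all 22, and Section 4.4 has the coordinating center announce when Stage 1 is closed. But the reply does not cover all of Section 12. Section 12.1.2 also says that 18 more patients are enrolled once 2 of 22 respond, and Section 12.9.1.2 says that Stage 2 proceeds on response. Both are written as sufficient conditions.

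A reader might also take the Section 5.1.2.2 review to be the only safety check in Phase II. It is not. Section 7.1 describes ongoing review of Grade 3 or 4 events, serious events, discontinuations and dose reductions, with escalation, and Section 11.2 gives the DSMB oversight of patient safety. Neither is tied to opening Stage 2.

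Nor do Sections 5.1.2.2 and 11.2 conflict on who reviews. Review by the sponsor and investigators can coexist with DSMB oversight, and the DSMB charter is not among the documents. The plan only fails to say how the one reaches the other.

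Two further points are fair. Treatment has no cycle limit, so all first-stage safety data most naturally means the data available at the review; that is why a data cut is needed. And patients in cycle 1 are assessed for toxicity during it, so 49% is a lower bound.

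**Conclusion.** The point holds as an omission that should be closed. The safety review is promised in Section 5.1.2.2, absent from the rules in Sections 12.1.2 and 12.9.1.2, and undefined in extent. Reading the sections together is possible but unwritten.

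If Section 12 is followed alone, up to 38 patients can be released while about 3 to 6 of the 22 Stage 1 patients are still in cycle 1. For a toxicity with a 10% cycle-1 rate, the chance of seeing at least two cases falls from 66% to between 49% and about 58% at 6 per month. The loss is moderate. The counts rest on even accrual at the rates in Section 13. The detection figures also rest on the assumed toxicity rate, the two-case threshold and the credit given to partial follow-up, none of which the protocol sets.

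**What to change.** Reconcile Sections 5.1.2.2, 12.1.2 and 12.9.1.2:
- In 12.1.2 and 12.9.1.2, make the Section 5.1.2.2 safety review an explicit second condition, beside the response count, for opening both Stage 2 and the MCL cohort.
- State the data cut. One option that follows the protocol's own Phase Ib hold is all treated Stage 1 patients through the end of cycle 1. Include any later replaced for response, because Sections 4.5 and 6.1 keep them for toxicity; the number may therefore exceed 22.
- State how the outcome of the review reaches the DSMB named in 11.2.
- Say that the waiver in 12.1.2 applies to response status only.

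The response trigger can be aligned in the same edit: 2/22 = 9.1%, which meets 12.1.2 but not the 10% in 12.9.1.2. That is a separate inconsistency.

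The cost is a few sentences and an accrual pause of about 4 to 5 weeks after the last Stage 1 patient starts, plus review time. The fifth week applies if the cut follows the dose-limiting toxicity definition in Section 5.1.4, which reaches 7 days past cycle 1. At 6 per month the pause defers about 5.5 to 6.9 entries (0.197 × 28 to 0.197 × 35). It adds no patients or procedures, and Section 5.1.2.2 already implies a pause of this kind.

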5.1.3 Required Blood Parameters and Other Investigations Prior to Each Treatment

Before the start of each treatment cycle, patients should be reassessed and the following criteria must be fulfilled:

- Karnofsky Score \geq 70 or ECOG Performance Status \leq 2

- ANC > 1000/dL
- Platelet count \geq 50,000
- Serum creatinine concentration $\leq 2.0 \times$ ULN or \leq baseline, or creatinine clearance >30 mL/min
- AST (SGOT) and ALT (SGPT) $\leq 3.0 \times$ ULN or $\leq 3.0 \times$ ULN in presence of demonstrable liver metastases
- Bilirubin concentration $\leq 2.0 \times$ ULN
- Recovery of any drug-related non-hematological toxicity to Grade 1 or less, unless otherwise indicated

5.1.4 Dose-Limiting Toxicity

A dose limiting toxicity (DLT) is defined as any toxicity not specifically included in section 5.1.4 that occurs within cycle 1. DLT is also defined as any toxicity, occurring up to 7 days after completion of cycle 1 that results in a delay of initiating cycle 2. For patients who discontinue study drug administration after Cycle 1, DLT will be defined as any toxicity not specifically included in section 5.1.4 that occurs within 30 days of the last dose of drug on study, in cycle 1 that is not related to disease progression.

DLTs include:

Hematologic dose-limiting toxicity will be defined as either Grade 4 neutropenia that does not resolve to \leq Grade 2 within \leq 7 days, any Grade 4 thrombocytopenia, or any Grade 5 hematologic toxicity. At least three patients in each cohort must be evaluable for hematologic toxicity.

Non-hematologic dose-limiting toxicity will be defined as any Grade 3, 4 or 5 non-hematologic toxicity, with the exception of:

- Grade 3 nausea or Grade 3 vomiting that occurs in the setting of inadequate compliance with supportive care measures specified in Section 5.1.7 and lasts for less than 48 hours.
- Grade 3 diarrhea that occurs in the setting of inadequate compliance with supportive care measures specified in Section 5.1.7 and lasts for less than 48 hours.
- Grade 3 dehydration that occurs in the setting of inadequate compliance with supportive care measures specified in Section 5.1.7 and lasts for less than 48 hours.
- Grade 3 acidosis or alkalosis that responds to medical intervention by returning to \leq Grade 2 within 48 hours.
- Isolated (i.e. no other abnormalities) Grade 3 elevation of liver function tests (LFTs) without associated clinical symptoms, lasting for \leq 5 days in duration.
- Isolated (i.e. no other abnormalities) Grade 3 elevation of amylase without associated clinical symptoms, lasting \leq 5 days
- Grade 3 hypocalcemia, hypokalemia, hypomagnesemia, hyponatremia, or hypophosphatemia that responds to medical intervention.

- Grade 3 hypercholesterolemia.
- Grade 3 hypertriglyceridemia
- Grade 2 Alopecia
- Grade 3 Constipation
- Grade 3 Fatigue

Management and dose modifications associated with the above adverse events are outlined in Section 6.3.

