Post cycle 1, colony stimulating growth factors (e.g., filgrastim, peg-filgrastim, and sargramostim) may be used in patients who experience hematological toxicity per

American Society of Clinical Oncology (ASCO) guidelines. Furthermore, patients who are not receiving such prophylaxis who experience febrile neutropenia (a DLT if occurring in Cycle 1) may receive treatment with colony stimulating factors at the Investigator's discretion. Neulasta should not be administered given that there is no data for co-administration of ACY-1215 with neulasta.

- **Thrombocytopenia:** Transfusion of platelets may be used if clinically indicated. Dose modification for thrombocytopenia is allowed in a manner consistent with the guidelines for dose modification (Section 6).

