6. DOSING DELAYS/DOSE MODIFICATIONS

6.1 Dose Delays

- Study drugs will be held until adverse event returns to \leq Grade 2.
- If interruption lasts for more than 14 days, study treatment will be discontinued.
- In patients who miss $>10\%$ of planned dose in the Phase II, but not the Phase Ib, data will be censored for response, but not for toxicity, and patients will be replaced for adequate response assessment.

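### Section 5.1.4 defines a dose-limiting toxicity by reference to itself with no grade limit, in conflict with its own graded list, and that list omits febrile neutropenia

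*Combined protocol and SAP*

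**What the plan says.** Section 5.1.4 of the combined protocol and SAP has three general limbs and then a graded list.

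- **Lead limb:** a DLT is "any toxicity not specifically included in section 5.1.4 that occurs within cycle 1".
- **Delay limb:** a toxicity up to 7 days after cycle 1 also counts if it "results in a delay of initiating cycle 2".
- **Discontinuation limb:** for patients who stop drug after cycle 1, the self-reference is repeated, with a 30-day window, a restriction to cycle 1 and an exclusion for disease progression.
- **Hematologic list:** "Hematologic dose-limiting toxicity will be defined as either Grade 4 neutropenia that does not resolve" to Grade 2 or less within 7 days, "any Grade 4 thrombocytopenia, or any Grade 5 hematologic toxicity".
- **Non-hematologic list:** toxicity of Grade 3 or above, less 12 exceptions. Three of the exceptions depend on compliance with "supportive care measures specified in Section 5.1.7 and lasts for less than 48 hours".

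Section 5.1.5, on supportive care, mentions in passing "febrile neutropenia (a DLT if occurring in Cycle 1". Section 5.1 ends at 5.1.6, so there is no section 5.1.7; the supportive-care content is in 5.1.5.

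The DLT count is used in three places. Section 12.1.1 uses it to decide cohort expansion, section 12.3.1.1 to stop enrollment into a cohort, and section 12.7 calls for DLT frequency to be summarized by dose cohort.

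**The concern.** A definition that excludes whatever is named in its own section removes the very events that the section names as DLTs. Because it has no grade limit, it also takes in trivial unlisted events. Staff therefore have to set the lead sentence aside and work from the list, and nothing in the text tells them to do so. The choice matters for a few realistic events, and the count that results is the assessed measure for the Phase Ib primary objective. Phase Ib safety data in turn inform the schedule taken into Phase II.

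**Working it through.** **The plan's own figure.** Two arms, each growing by 3 + 3 + 4 = 10 patients, give 2 × 10 = 20. This matches the stated Phase Ib maximum, and nothing below alters it.

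**Four cycle 1 events under three readings.** Assume that none of them delays cycle 2. Reading A is the lead sentence taken literally. Reading B takes the self-reference to mean only the exceptions. Reading C uses the graded list with its exceptions.

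| Event | A | B | C |
|---|---|---|---|
| Grade 4 thrombocytopenia | no (it is listed) | yes | yes |
| Grade 1 cough | yes | yes | no |
| Grade 3 anemia | yes | yes | no |
| Febrile neutropenia, with Grade 4 neutropenia resolving to Grade 2 or less within 7 days | yes (it is unlisted) | yes | not a hematologic DLT |

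Reading B repairs the first row only. Reading C gives a workable rule, but on the last row it disagrees with section 5.1.5, which makes febrile neutropenia in cycle 1 a DLT without any condition on duration.

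**Is the anemia row realistic?** Sections 2.2.15 and 7.3.2 report possibly related Grade 3 anemia at 160 mg, the dose used here. Those were myeloma patients on a different schedule, observed over their whole treatment. This shows that the event can occur; it does not give a cycle 1 rate.

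**Does Grade 3 anemia delay cycle 2?** Section 6.1 points that way: "Study drugs will be held until adverse event returns to" Grade 2 or less. But the cycle-start criteria (section 5.1.3, Required Blood Parameters) contain no hemoglobin threshold, and their recovery line covers non-hematological toxicity only. Table 2 in section 6.3.1 has no anemia row. The answer is not settled, so the delay limb cannot be relied on to capture the event.

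**Where one reclassified patient reverses a decision.** Let x be the number of DLTs before that patient is counted.

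- Section 12.1.1 expands from 3 to 6 if x ≤ 1, and from 6 to 10 if x ≤ 2. Moving to x + 1 reverses the decision at 1 → 2 of 3 and at 2 → 3 of 6.
- Section 12.9.1.1 uses strict inequalities. x/3 < 1/3 requires x = 0, and x/6 < 2/6 requires x ≤ 1. The decision reverses at 0 → 1 of 3 and at 1 → 2 of 6.

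**Effect on the reported frequency.** One patient is 1/3 = 33, 1/6 = 17 or 1/10 = 10 percentage points in cohorts of 3, 6 and 10. This is simply one patient's share of the cohort, not an estimate of how often reclassification would happen.

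**The case against.** The strongest reply is that this is an editorial slip. The graded criteria follow directly after the general limbs and are introduced as DLTs, so no sensible reader would decide that Grade 4 thrombocytopenia does not count. The numbers 5.1.2 and 5.1.3 are each used twice and 5.1.7 does not exist, which suggests a cross-reference lost in renumbering. On febrile neutropenia the protocol gives only one explicit answer. This version is a Phase II amendment, so Phase Ib counting may be over, and section 7.3.4 reports no DLTs among patients on monotherapy in the earlier study.

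Much of this stands. A reader might infer that the definition cannot be applied at all; the graded list shows otherwise. A reader might also take the exception "Grade 2 Alopecia" as proof that there is no Grade 3 floor. It is redundant, but the sentence introducing the exceptions states the floor for non-hematologic events, and a stray bullet does not cancel it. Nor is the protocol silent on febrile neutropenia, since section 5.1.5 speaks to it.

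What the reply does not remove is the disagreement between the lead sentence and the list on anemia, and between the list and section 5.1.5 on short-lived febrile neutropenia. The non-hematologic rule might be thought to catch the latter, but Table 2 puts febrile neutropenia under its own heading, separate from the other non-hematologic toxicities.

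**Conclusion.** The definition is wrong as written, and the matter is minor. The likely intent is recoverable from the list, but an operative rule should not have to be inferred, and two realistic events are classified differently depending on which text is followed. One such patient can reverse an expansion decision at the counts shown, and which counts those are depends on whether section 12.1.1 or section 12.9.1.1 governs.

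No probability is claimed, because the documents report no cycle 1 toxicity rates for this schedule. A reader might infer that a Phase Ib decision or the Phase II schedule was in fact affected. The documents show no patient whose classification was in doubt, so that does not follow. Nor can one say that persistent Grade 3 anemia is certain to count through the delay limb; section 6.1 suggests a hold, but the cycle-start criteria and Table 2 do not address anemia.

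**What to change.** Amend section 5.1.4 as follows.

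1. Replace the lead sentence: a DLT is a toxicity occurring within cycle 1 that meets the hematologic or non-hematologic criteria below and is not one of the listed exceptions.
2. Keep the limb for toxicity that delays cycle 2.
3. In the discontinuation limb, replace only the self-reference with the same criteria. Keep its cycle 1, 30-day and not-due-to-progression limits; dropping the cycle 1 limit would widen the definition to later cycles.
4. Add febrile neutropenia to the hematologic list, to match section 5.1.5.
5. Change 5.1.7 to 5.1.5 in the three exceptions that cite it.

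Under this wording Grade 3 anemia counts only if it does delay cycle 2; the investigators can add it to the list if they want it counted in any case. If Phase Ib DLTs have already been counted, the study report should state which definition was applied.

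The cost is wording in one section and possibly one sentence in the report. It adds no patients, visits or tests.
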